#### 11.2.1 SAE Reporting

Following the subject's written consent to participate in the study, all SAEs, whether related or not related to study procedures, must be collected, including those thought to be associated with protocol-specified procedures. If applicable, SAEs must be collected that relate to any later protocol-specific procedure (such as follow-up skin biopsy).

The investigator should report any SAE occurring after these time periods that is believed to be related to study drug or protocol-specified procedure. An SAE report should be completed for any event where doubt exists regarding its status of seriousness.

If the investigator believes that an SAE is not related to study treatment, but is potentially related to the conditions of the study (such as withdrawal of previous therapy, or a complication of a study procedure), the relationship should be specified in the narrative section of the SAE Report Form.

SAEs, whether related or unrelated to the study intervention must be reported to the sponsor agent within 24 hours. SAEs must be recorded on the SAE Report Form;

If only limited information is initially available, follow-up reports are required. (Note: Follow-up SAE reports should include the same investigator term(s) initially reported.) If an ongoing SAE changes in its intensity or relationship to study intervention or if new information becomes available, a follow-up SAE report should be sent within 24 hours to the sponsor (or designee) using the same procedure used for transmitting the initial SAE report. All SAEs should be followed to resolution or stabilization.

#### 11.3 Non-Serious Events

A non-serious adverse event is an AE not classified as serious.

## 11.3.1 Non-Serious Adverse Events (NSAEs) Collecting and Reporting

The collection of non-serious adverse event (NSAE) information will begin at initiation of study treatment.

Non-serious AEs will be followed to resolution or stabilization, or reported as SAEs if they become serious. Follow-up is also required for non-serious AEs that cause interruption or discontinuation of study treatment, or those that are present at the end of study treatment as appropriate.

Non-serious Adverse Events are provided to local IRB and the sponsoring agent via annual safety reports (if applicable), and interim or final study reports.

#### 11.3.1.1 Anticipated Risks

While the study anticipates minimal risks, the following outlines any potential minimum risk to subjects:

i. Breach of Confidentiality: Data obtained using information from medical records, poses minimum risk. All procedures in which information is being obtained will be conducted per standard of care. There is a risk that a patient's privacy may not be protected. This risk is uncommon.

ii. Discomforts: Persons receiving treatment for Vulvar Intraepithelial Neoplasia can anticipate the following risks: infection, dysuria, burning, adhesions, light bleeding, and discharge. Participants could expect to experience pain and discomfort following surgery for approximately 1 week. Participants should refrain from exercise and sexual intercourse in the two weeks following surgery in order to avoid addition discomfort.

iii. Recurrence: Current treatment for vulva-sparing has a recurrence rate of 25-50% of return disease. Recurrence, left unmanaged, could lead to cancer of the vulva, vagina, or the cervix.

Participation in this study will not have any influence on the patient's current treatment. The study may include risks that are unknown at this time.

#### 12. Data Collection and Confidentiality

This study will obtain approval for conduct through the Colorado Multiple Institutional Review Board (COMIRB) for research involving human subjects. All patients within the Gynecologic Oncology clinic at the University of Colorado Cancer Center who meet the study criteria will be considered eligible for the study. We will not enroll any vulnerable populations as defined by ethical guidelines, but will follow participants that may become pregnant during the 12 month participation duration. Potential participants will be screened by the PI/Co-I and the research team and approached for consent. Consent will occur prior to the initiation of any study procedures at a scheduled clinic visit in the Gynecologic Oncology clinics of participating sites. Potential participants will be provided a private setting for inperson consent and will be adequately informed of the study intent, requirements, and potential risks and benefits. Patients will also be informed that any participation is voluntary and will not affect any clinical care they are to receive. Research staff providing consent will be certified in Collaborative Institutional Training Initiative (CITI) and Human Insurance Portability and Accountability Act (HIPAA) trainings for ethics and human protection. Patients will have time to review the consent and ask any questions prior to signing consent.

For secondary sites, additional approval will be obtained by the institution's local IRB.

# 12.1 Data Collection Tools

# 12.2 Data Integrity and Protection of Confidentiality

#### 13. Study Monitoring

There are no investigational treatments associated with consent into the study, as both treatments are currently approved for the treatment of VIN in women 18-89 years old. Each study site will obtain local IRB approval. The Primary Investigator will be responsible for monitoring the study for unanticipated problems and SAEs and report them to lead and local IRBs as appropriate. No interim analysis will be conducted.

## 13.2 Safety Monitoring Plan

The Principal Investigator (PI) will be responsible for executing the safety monitoring plan, and complying with all reporting requirements to local and federal authorities. This safety monitoring plan will be conducted via the use of a safety officer. The safety officer will be a 3rd party reviewer, affiliated with the University of Colorado Denver but with no direct affiliation to the research study or the sponsor. The safety officer will be identified by the PI prior to initiation of the study. This study does not require a full data safety monitoring board since there are no investigational devices or treatment interventions in this study.

The safety officer is responsible for providing an independent safety review and trial guidance during the course of the study. A summary of the safety officer's activities is as follows:

- Review the initial protocol and make recommendations towards safety concerns
- Review study recruitments and enrollments over course of the study
- Review procedures for data quality control over the course of the study
- Set the parameters for monitoring review, and interim safety analysis
- Ongoing review of all serious adverse events (SAEs), unanticipated problems (UAPs) and reportable adverse events (AEs)
- Has the authority to close and/or suspend trials for safety conduct issues
- May submit recommendations for corrective actions to the PI to address safety concerns

Per the Safety Monitoring Plan, SAEs, UAPs and reportable AEs are reported to the safety monitor, IRB and the sponsor per study protocol. All SAEs, UAPs and reportable AEs are to be reported to the safety monitor within 5 business days of receiving notification of the occurrence. Non-reportable AEs will be reported in the safety monitoring report provided to the safety officer every 12 months.

Each subject's treatment outcomes will be discussed by the Investigators and Clinical Research Coordinators (CRCs) at regularly scheduled disease-oriented working group meetings. Data regarding number of subjects, significant toxicities, dose modifications, and treatment responses will be discussed and documented in the meeting's minutes.

The PI will provide a safety report to the safety monitor on a 12-month basis. The report will include a protocol summary, current enrollment numbers, summary of data to include specific SAEs, UAPs and AEs, all protocol deviations, and protocol amendments. The safety report will also include, if applicable, the results of any efficacy data analysis conducted, as well as any sponsor-related safety reports. Results and recommendations from the review of this annual report by the safety monitor will then be submitted by the site to the IRB of record at the time of continuing review.

The coordinating site (UCD) is responsible for organizing and conducting monthly teleconferences with all participating sites. The PI will also be responsible for including data from all of the participating sites within the overall trial's annual safety report to the safety officer to include minutes from monthly PI teleconferences. Research staff at the University of Colorado Denver Department of Obstetrics and Gynecology will conduct monitoring internally of the coordinating site internally and for all secondary sites outside the institution. Each participating site will be responsible for submitting the results and recommendations from the annual safety review to their IRB of record at the time of continuing review.

## 14. Statistical Analysis

A per protocol analysis will be conducted. Participants receiving treatment per protocol will be included in the final analysis. Investigators will not have the option to change treatment assignment.

Descriptive statistics using means, frequencies, and percentages will be computed to describe the study population. Participant data will be analyzed employing the per protocol approach. Student's *t*-test (for continuous variables) and chi-square tests (for categorical variables) will be used to compare the two groups for demographic, and secondary outcome variables: pain, scarring, QOL scores. For the primary outcome measure rate of recurrence for each of the study endpoints, 3 months, 6 months and 12 months will be calculated per treatment arm and compared with initial bivariate analysis using chi-square analysis. Additional predictors for recurrence (pain, scarring, sexual function, and general wellness) will be compared similarly with chi-square for categorical variables and t-tests for continuous variables. Potential covariates (age, race, previous disease, etc.) will also be analyzed using bi-variate analysis. Variables found to be significant in the bivariate analysis will be included in multivariable analysis using logistic regression. Logistic regression models will be used to identify significant independent predictors associated with recurrence for each treatment arm. The logistic model will allow for control of study covariates. A p-value of <0.05 will be used to demonstrate statistical significance. IBM SPSS version 22 will be used for all statistical analyses.

Incidence of AEs and SAEs will be compared between treatment arms using chisquare analysis. A p-value of <0.05 will be used to demonstrate statistical significance.

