### 3. Preliminary Studies and Research Centers

#### 3.1 Principal Investigator and Research Center

#### 4. Outcome Measures

Primary Outcome: The primary outcome of this study is recurrence rates of dysplasia within 12 months of treatment. Rates of recurrence will be compared for CO2 laser ablation and ultrasonic aspiration, stratifying groups based on HPV and multifocal disease status. Recurrence will be assessed at 3, 6, and 12 months following treatment. Recurrence will be determined by repeat visual exam and colposcopy (followed by biopsy as warranted) at each of the follow-up visits. Those with recurrence will be discontinued from the study and receive appropriate treatment for their recurring dysplasia, per standard of care (SOC).

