#### 4.1. Study Endpoints

Patients will be enrolled at participating centers prior to receiving treatment for their VIN II/III. Baseline assessments will include all study surveys and collection of demographic and clinical data.

Pain and scarring will be assessed within the first 6 weeks following treatment. Participants will be followed at 3, 6, and 12 months for recurrence. Participants will be discontinued from the study at time of recurrence, or at the completion of 12 months follow-up. Total participation is 12 months duration.

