## 6.2 Sample Size

Based on previous studies, approximately 37.5% of patients will reoccur within 12 months with traditional treatment (CO2 laser). [5, 7-13] We can detect a 60% reduction of recurrence to a rate of 15% at 80% power and an alpha of 0.05 with 62 patients per arm. [3] We will enroll an additional 13 patients per arm (n=75 per arm, 150 total) to account for noncompliance, lost to follow-up or misclassification diagnosis.

Approximately 75% of participants will be recruited at the coordinating site, University of Colorado Denver. The other 25% of participants will be recruited at the secondary sites Regional West Medical Center, and The University of Oklahoma are the secondary sites recruiting participants.

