# 15.1.2 Subject Withdrawals

All participant documentation up until study withdrawal will be maintained and used for data analysis. In the event a participant is lost to follow-up, 3 documented attempts will be made to contact the participant to conduct an end of treatment visit. If after 3 attempts, the participant still does not return, a certified letter noting withdraw from study should be sent to the participant. The study coordinator will maintain a return receipt for such. Additionally, the study coordinator should send a self-addressed package to the participant for return of any study medications and/or study documents.

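### The chi-square comparison of raw recurrence proportions has no method for women lost before 12 months; a prespecified life-table 12-month risk would close the gap at little cost

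*Combined protocol and SAP*

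**What the plan says.** Section 4 states that "The primary outcome of this study is recurrence rates of dysplasia within 12 months of treatment". Section 6.2 plans on the same cumulative scale: "approximately 37.5% of patients will reoccur within 12 months with traditional treatment (CO2 laser"), with the effect given as "We can detect a 60% reduction of recurrence to a rate of 15"%. The size stated for this effect is 62 women per arm, for 80% power with alpha 0.05. The section then adds 13 women per arm, to 75, for noncompliance, loss to follow-up and misclassified diagnosis together.

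In Section 14, rates at "3 months, 6 months and 12 months will be calculated per treatment arm and compared with initial bivariate analysis using chi-square analysis". Then "Logistic regression models will be used to identify significant independent predictors associated with recurrence for each treatment arm". No survival or life-table method is named.

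Four other provisions bear on incomplete follow-up:
- Section 4.1: "Participants will be discontinued from the study at time of recurrence".
- Section 11.2 also discontinues women who have a serious adverse event.
- Section 15.1.2: "All participant documentation up until study withdrawal will be maintained and used for data analysis".
- Sections 9 and 14 define the per-protocol set by treatment received, not by completed follow-up. A correctly treated woman who is clear at 6 months and then lost therefore stays in the analysis set without a 12-month outcome.

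Sections 4 and 14 refer to a 3-month recurrence assessment. The visit list in Section 8 goes from 4-6 weeks to 6 months.

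**The concern.** Chi-square and logistic regression take a binary outcome and ignore follow-up time. A woman lost after a clear 6-month visit must either be left out or be given an outcome, and the plan chooses neither. The two simple choices err in opposite directions:
- Leaving her out keeps every early recurrence but removes event-free women, so the risk is overstated.
- Counting her as recurrence-free ignores the recurrences that would have appeared later, so the risk is understated.

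Neither choice delivers what Section 15.1.2 promises, which is to use the follow-up she did contribute.

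If loss differs between arms, so does the distortion, and it enters the treatment comparison. Unequal loss is possible here. Only the statistician is described as blinded (Section 7.1), and the arms are expected to differ in pain and scarring (Sections 2.1 and 11.1). A denominator left open can also be chosen after the data are seen.

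**Working it through.** **The plan's sample size.** Take 37.5% v 15%, two-sided alpha 0.05 (sidedness is not stated) and 80% power. The pooled mean is 0.2625, and

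n = [1.96·√(2·0.2625·0.7375) + 0.8416·√(0.375·0.625 + 0.15·0.85)]² / 0.225² = (1.2196 + 0.5063)² / 0.050625 = 58.8, so 59 per arm.

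The stated 62 is slightly conservative (power 82.1%). The allowance is 13/75 = 17.3%, and 62/(1 − 0.1733) = 75.

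**Assumptions not in the documents.** Half of the 12-month recurrences are found by 6 months. Loss occurs after a clear 6-month visit and is unrelated to later recurrence. The whole 17.3% is loss to follow-up. The last is an upper bound on the allowance, which also covers two other causes.

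**Expected 12-month estimates with 17.3% lost in both arms**

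| Step | Laser | Aspiration |
|---|---|---|
| Recurred by 6 months | 0.1875 | 0.075 |
| Clear at 6 months | 0.8125 | 0.925 |
| Lost later (× 0.1733) | 0.1408 | 0.1603 |
| Late recurrences seen (× 0.8267) | 0.1550 | 0.0620 |
| All recurrences seen | 0.3425 | 0.1370 |
| Lost women dropped | 0.3425/0.8592 = 39.9% | 0.1370/0.8397 = 16.3% |
| Lost women counted as free | 34.3% | 13.7% |
| Life table | 37.5% | 15.0% |

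The life-table risk is 1 − (1 − early risk)(1 − late risk among women still followed). For laser this is 1 − 0.8125·(1 − 0.1550/0.6717) = 1 − 0.8125·0.7692 = 0.375.

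The relative risks are 16.3/39.9 = 0.41 (dropped) and 13.7/34.3 = 0.40 (counted free), against a true 0.40.

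**Error rates by simulation** (75 per arm, same model; the life-table test is a Wald test with Greenwood variance)

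| True risks | Late loss, laser v aspiration | Dropped | Counted free | Life table |
|---|---|---|---|---|
| 37.5% both (type I error) | 17.3% both | 5.1% | 5.0% | 5.5% |
| 37.5% both (type I error) | 10% v 25% | about 6% | about 6.5% | about 5.4% |
| 37.5% both (type I error) | 5% v 30% | about 7.6% | about 9% | 5.5% |
| 37.5% v 15% (power) | 17.3% both | 85.6% | 85.2% | 86.2% |
| 37.5% v 15% (power) | 25% v 10% | about 91% | about 78% | about 86% |
| 37.5% v 15% (power) | 10% v 25% | about 79% | about 91% | about 86% |

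**A different dropout model** (constant recurrence hazard, exponential dropout from treatment onward) agrees on direction. With dropout of 25% v 10% and no true difference, type I error is 8.3% when lost women count as free, 5.2% when dropped and 5.3% by life table. With the planned effect, power is 70%, 87% and 84% respectively.

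**If only women attending at 12 months were compared.** The risks become (0.375 − 0.1875)/0.8125 = 23.1% and (0.15 − 0.075)/0.925 = 8.1%. About 50 v 57 women remain, and power is about 59%. Even with no loss it is 68%, against 89% for the cumulative rate.

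**The case against.** The strongest defence is that the damage is small unless loss is markedly unequal. With equal loss, type I error stays at 5%, the relative risk is 0.40-0.41, and the life table gains under one point of power, because Section 8 lists recurrence visits only at 6 and 12 months. Even at 15% v 20% loss, type I error is about 5%. The documents give no basis for gaps as wide as 5% v 30%. All of this stands, and it limits the claim.

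Three stronger readings are tempting, and the documents do not support them:
- *That women who leave at recurrence are mishandled.* Sections 2, 4 and 6.2 describe recurrence within 12 months, which is cumulative. A woman who leaves at recurrence has a known outcome, and a cumulative chi-square counts it correctly. The 59% power figure applies only if the 12-month rate is taken among attenders. Section 14 does not say that; its visit-by-visit wording merely fails to exclude it.
- *That a life table is the only route to an unbiased comparison.* Imputation, weighting, or a stated denominator with sensitivity analyses could also serve. A life table is itself unbiased only if censoring is unrelated to recurrence risk, which withdrawals for serious adverse events may violate. It does not undo the per-protocol exclusions either.
- *That the plan expects 17% loss.* The allowance pools three causes, and some of those women would be excluded rather than censored.

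What the defence does not answer is that the plan keeps lost women in the analysis set, promises to use their data, and names no method for doing so.

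**Conclusion.** The concern holds in a limited form. The primary analysis has no rule or method for women lost or withdrawn between recurrence assessments. At the upper-bound loss of 17.3%, the unstated choice moves the laser estimate from 37.5% to 39.9% or 34.3%, and the aspiration estimate from 15% to 16.3% or 13.7%. The comparison between arms is essentially intact under equal loss. Under unequal loss, type I error reaches about 7.6% or 9% at 5% v 30%, and power differs by about 13 points according to the choice made at 25% v 10%. The life table is nearly unaffected in both cases (5.5% and about 86%).

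These sizes rest on the assumed timing of recurrences, on loss unrelated to later recurrence, and on loss rates that the documents do not give. This is worth correcting before analysis because the better method is almost free; it does not show that the planned trial must fail.

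**What to change.** In Section 14:
1. Define the primary endpoint as the cumulative 12-month recurrence risk, with a recurrence counted at all later time points. This rules out an attenders-only rate.
2. Make the primary comparison the difference in life-table (Kaplan-Meier or discrete-time) 12-month risk. Each woman contributes up to her last recurrence assessment.
3. Name one test of that difference, stratified by HPV and multifocal status. One option is a stratum-weighted difference with Greenwood variance and weights fixed in advance. A log-rank test compares whole curves rather than the 12-month risk, so it should not be left as an alternative.
4. Assign assessments to their nominal visits, so that a woman seen clear early in the ±30-day window is not censored before 12 months.
5. Keep the chi-square as supportive, with its denominator stated.
6. Add a sensitivity analysis for informative loss, including withdrawals for serious adverse events.
7. Reconcile the 3-month assessment in Sections 4 and 14 with the visit list in Section 8; the life-table intervals depend on it.

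The cost is revised wording and a little more analysis work. The new analysis relies on non-informative censoring, which item 6 probes. The sample size does not need to rise: at 75 per arm with 17.3% loss in both arms, power is about 86%.

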## 1.1 Significance

Vulva preserving treatments are necessary women with dysplasia in order to maintain function and decrease discomfort typical with a vulvectomy. [4] However, these less invasive techniques have a high recurrence rate. Recurrence is particularly greater for those with HPV and multifocal disease. [5, 6] Women must follow these treatments with long-term surveillance, which often leads to repeat treatment and eventually dysfunction and psychological morbidity. [5] Studies have found that recurrence rates with CO2 laser ablation can range from 25-50% recurrence, while rates for ultrasonic aspiration have been found to range from 22-35% recurrence. [5, 7-13] [2, 14]

Von Greugenigen's study failed to limit the study to women with high-grade dysplasia only. As a result, the final analysis failed to meet statistical power. No RCT has been conducted since looking at reoccurrence difference and QOL outcomes associated with ultrasonic aspiration vs. CO2 laser.[3]

We propose a similar study by which to randomize women to either CO2 laser ablation or ultrasonic aspiration for the treatment of vulvar dysplasia. We estimate that we need 150 patients to achieve statistical power. We will similarly evaluate patients at 3, 6 and 12 months to assess for recurrence and pain. We will also have patients complete quality of life (QOL) surveys to assess which differences in wellness and function following treatment at baseline, 6, and 12 months.

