# 6.3 Research Design and Duration

This study will employ a randomized controlled trial (RCT) design. This is a phase III study to determine the effectiveness of a more targeted treatment therapy for VIN II/III (comparing ultrasonic aspiration versus CO2 laser ablation). Potential participants will be identified through the gynecological clinical practices following diagnosis of VIN II/III and will be randomized (1:1) to one of the treatment therapies. Randomization will be stratified for multi-focal disease and HPV status.

Participants will be followed for 1 year following initial treatment for recurrence of vulva dysplasia. Study events will be documented on the study clinical research forms for each visit. The study will continue until 150 participants have completed procedures, which is expected to take approximately 3 years.

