All study treatment will be conducted by study-trained investigators only. The investigators chosen to participate in the study will all be board-certified gynecologists and will not include providers in-training. Gynecologists are trained to perform vulva sparing treatment in the clinical setting. All investigators elected for this study have a minimum of 3 years of clinical practice following fellowship. The coordinating site will host an in-service for all participating investigators prior to initiation of the study. The in-service will review the standard operating protocols of both devices. Ongoing monitoring and site visits by the PI will also be conducted to insure investigator compliance. In addition, secondary analysis will examine treatment differences per investigator.

Block randomization will be conducted using randomization statistical software. Research personnel will login into the study database and enter information for block randomization on the day of surgery. The randomization software associated with the REDCap data tool will provide the research team with the treatment assignment. Stratification variables will include multifocal disease and HPV status. The statistician responsible for statistical analysis will be blinded to the treatment received.

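### Section 14 omits the stratified recurrence comparison that section 4 promises, and its screened logistic step fixes no sound adjusted treatment effect

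*Combined protocol and SAP*

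**What the plan says.** Section 1.1 gives the reason for treating two factors as important: "Recurrence is particularly greater for those with HPV and multifocal disease". The design acts on it. Section 6.3 says "Randomization will be stratified for multi-focal disease and HPV status", and section 7.1 repeats "Stratification variables will include multifocal disease and HPV status". Section 4, defining the primary outcome, says the arms' recurrence rates will be compared "stratifying groups based on HPV and multifocal disease status".

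Section 14 sets out the analysis. Recurrence rates at 3, 6 and 12 months "will be calculated per treatment arm and compared with initial bivariate analysis using chi-square analysis". No strata are mentioned. Covariates are handled as follows: "Potential covariates (age, race, previous disease, etc.) will also be analyzed using bi-variate analysis". A second candidate group is added: "Additional predictors for recurrence (pain, scarring, sexual function, and general wellness) will be compared similarly with chi-square" (t-tests where continuous). Selection is by p-value: "Variables found to be significant in the bivariate analysis will be included in multivariable analysis using logistic regression". The logistic models are described as finding predictors of recurrence for each arm, and the next sentence says the model permits control of covariates. No treatment term, fixed covariate set or effect estimate is specified.

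**The concern.** There are two linked defects.

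- **The stratified comparison is missing.** The factors that govern allocation, and that the protocol calls prognostic, do not appear in the analysis section. At best they fall under the open end of the covariate list and reach a model only if they happen to pass a p<0.05 screen.
- **The logistic step does not fill the gap.** Its candidates include pain (assessed 7-10 days after treatment) and scarring (about 4-6 weeks after). Sexual function and wellness are measured at baseline, 6 and 12 months, and section 14 does not say which measurement is used. The description of the models has two readings. Fitted within each arm, they contain no treatment term and cannot estimate a between-arm effect. Fitted jointly, a screened-in pain or scarring term adjusts the treatment effect for a consequence of treatment.

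At stake are a little power that the stratified design has already paid for and, more seriously, the freedom to decide after seeing the data which comparison is primary and what the adjusted result is.

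**Working it through.** **Inputs from the documents.** Recurrence 37.5% (laser) and 15% (aspiration), 62 per arm, 80% power, alpha 0.05 (section 6.2); 1:1 allocation stratified by two factors (sections 6.3 and 7.1); scarring about 30% with laser and under 5% with aspiration (section 11.1). Two-sided testing is assumed because sidedness is not stated.

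**The plan's own figure.** With mean rate 0.2625,

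n = [1.960 × √(2 × 0.2625 × 0.7375) + 0.842 × √(0.375 × 0.625 + 0.15 × 0.85)]² / 0.225² = (1.220 + 0.506)² / 0.0506 ≈ 58.8, so 59 per arm.

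The plan's 62 is not reproduced exactly. For an uncorrected chi-square it is slightly generous: exact power at 62 per arm is 82.7%. This is a separate small matter, and 82.7% serves as the benchmark below.

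**Unstratified against stratified test.** The two statistics, each compared with 3.84, are:

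- Pearson: (p̂₁ − p̂₂)² / [p̄(1 − p̄)(1/n₁ + 1/n₂)]
- CMH, summing over strata s: [Σ(x₁ₛ − n₁ₛmₛ/Tₛ)]² / Σ[n₁ₛn₂ₛmₛ(Tₛ − mₛ) / (Tₛ²(Tₛ − 1))], where x₁ₛ is events in one arm, mₛ total events and Tₛ total women.

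The Pearson variance still contains the between-stratum variation that balanced allocation has removed from the difference, so the test is conservative. The size was found from 100,000 simulated trials of 124 women per scenario, balanced within four strata, without continuity correction. Prevalences and odds ratios are assumptions. For HPV 70% and multifocal 50%:

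| Odds ratio, each factor | Chi-square type I error | Chi-square power | CMH power | Loss (points, from unrounded values) |
|---|---|---|---|---|
| 2 | 4.8% | 83.1% | 84.0% | 0.9 |
| 3 | 4.0% | 83.9% | 85.8% | 2.0 |
| 4 | 3.5% | 84.3% | 87.2% | 2.9 |

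CMH type I error is 4.9-5.1%. A repeat with another seed moved no figure by more than 0.5 points. At other assumed HPV/multifocal prevalences the losses at odds ratios 2/3/4 are 0.6/1.5/2.3 (90%/50%), 0.9/2.3/3.3 (50%/30%) and 0.7/1.9/2.6 (80%/40%). At odds ratio 1 the loss is nil (−0.1).

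**Would the screen recover the strata?** Same model (70%/50%, 37.5% against 15%), bivariate chi-square at p<0.05:

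| Passing the screen | OR 2 | OR 3 | OR 4 |
|---|---|---|---|
| HPV, arms pooled | 24% | 50% | 66% |
| Multifocal, arms pooled | 33% | 66% | 83% |
| Both, arms pooled | 8% | 33% | 55% |
| Both, laser arm only | 4% | 18% | 33% |
| Both, aspiration arm only | 1% | 5% | 9% |

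**Models within each arm.** Expected events are 62 × 0.15 = 9.3 with aspiration and 62 × 0.375 = 23.3 with laser. A multivariable model on about nine events is barely estimable and has no treatment term.

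**Joint model that may include scarring.** Assume no true treatment effect (recurrence 37.5% in both arms, odds ratio 1.00), scarring 30% against 5%, and an unmeasured normal risk factor with log-odds slope 0.5 or 1.0 on both scarring and recurrence. If scarring is always in the model, the treatment odds ratio becomes 1.06 or 1.21 (2 million records). With the screen (20,000 trials of 62 per arm), scarring enters in 7.4% or 28.1% of trials. In those trials the median treatment odds ratio is 0.82 or 0.87 without scarring and 1.09 or 1.21 with it.

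**The case against.** The strongest reply is that little is lost. The chi-square is valid, conservative and above the planned power in every scenario, and the loss depends wholly on assumed prevalences and odds ratios. Section 1 links HPV to all the causes it lists. That points towards high HPV prevalence, and the 90%/50% pair shows the smallest losses of the four. If all 75 per arm are evaluable, the 70%/50% loss is only about 0.5 to 2 points, with chi-square power near 90%. This stands: the power argument alone would be a minor remark.

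The screening result also looks worse when both factors must pass. At least one passes in about 49%, 83% or 95% of trials. But a sound analysis needs both factors, and each alone is often dropped at odds ratios of 2 or 3.

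The scarring example rests on an unmeasured shared risk factor for which the documents give no evidence. At slope 0.5 the pass rate is close to the nominal 5%, and the medians among screened-in trials mix selection with conditioning. The always-included figures, 1.06 and 1.21, are the cleaner measure. The shift goes against aspiration, so it would not flatter the sponsor's hypothesis. The example shows that distortion is possible, not how large it will be.

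Read literally, section 14's models are prognostic ones fitted by arm, where a post-treatment predictor is no error in itself. On that reading, though, the plan has no adjusted treatment effect at all. Section 4's phrase about stratifying might refer to allocation, but its sentence concerns comparing rates, so an analysis commitment is the more natural reading. Finally, section 7.1 blinds the analysing statistician to treatment. That reduces the risk of a data-driven choice without removing it.

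**Conclusion.** The point holds and should be corrected. It does not invalidate the primary test. Across the four assumed prevalence pairs and odds ratios of 2 to 4, ignoring the strata costs 0.6 to 3.3 points of power at 62 per arm, with no inflation of type I error from this source. These figures apply to the uncorrected chi-square. The main weight rests on the text and needs no assumption: sections 4 and 14 describe different primary comparisons, the randomization factors are not named in the analysis, and neither reading of the logistic step pre-specifies a sound adjusted treatment effect. Confidence is medium, because every size quoted depends on prognostic strengths the documents do not give.

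**What to change.** In section 14:

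1. Name one primary analysis of 12-month recurrence. Either use a CMH test stratified by HPV and multifocal status, or one logistic model in both arms together with treatment, HPV and multifocal terms retained whatever their p-values. Report the treatment effect with a 95% confidence interval.
2. Limit further covariates in that model to baseline variables listed in advance, for example age, previous disease and baseline sexual function. Exclude pain, scarring, and post-baseline sexual function and wellness.
3. State whether the predictor models are fitted by arm or jointly, give the time point of each predictor, and label these models exploratory.
4. Make sections 4 and 14 say the same thing.

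The cost is analysis wording only. No extra women or visits are needed, and stratifying does not call for a larger sample. Both factors must be entered to randomize. HPV status is not named in section 4's clinical data list, so confirm that the values used for allocation are kept in the analysis dataset.
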